6. INCLUSION AND EXCLUSION CRITERIA*

Aim 1 Individual Stakeholder Interviews (in place of Focus Groups)

Inclusion criteria

Patients from 3 participating sites with a diagnosis of OA in the knee and/or hip, identified by the surgeon or designated staff.

Caregivers or trusted others of patients with OA in the knee and/or hip from 3 participating sites, identified by the surgeon, designated staff or by patients participating in the patient interviews.

Patients must be 18 years of age or older and able to provide informed consent.

Exclusion criteria

Inflammatory arthritis, such as rheumatoid or psoriatic arthritis

Pregnant women

Prisoners

Non-English speaking subjects as the interview guide and tools for patient review are only available in English.

Aim 2 and 3

Inclusion Criteria

Aim 3 modification: We proposed to PCORI (and they agreed) that we expand beyond “new” patients as these are only patients who are new to the surgeon’s practice. We did this for staff training simplicity, not because these are the only appropriate patients to use the report.

*NOW: Enroll all patients who are not “follow-up” appointments to surgery or other treatment, so that both (a) patients **new to the practice** (already in ISP) and (b) existing patients who have seen surgeon before but are **here for a new evaluation** are eligible.*

Patients must be 40 years of age or older and able to provide informed consent.

Because only new office patients are enrolled, patients enrolled in Aim 2 will not be eligible for enrollment in Aim 3. (Even with the updated definition of “new” patients, patients enrolled in Aim 2 will not be eligible for enrollment in Aim 3.)

Non-English (Spanish) speaking subjects will be included in aim 2 of the study; Non-English speaking patients will not be included in Aim 3 (with funder approval). The OA Careplan + Support program (now called A.S.K. Coaching) will only be available with an English speaking health educator and we learned in Aim 2 that <1% of eligible patients were primarily Spanish language speakers.

Exclusion criteria

Inflammatory arthritis, such as rheumatoid or psoriatic arthritis

INVESTIGATOR STUDY PLAN

12.14.2021

Recent knee or hip injury as purpose for visit

Contraindications to TJR surgery including co-existing conditions that negate functional improvement with OA treatment/surgery and terminal illness with a life expectancy of less than 6 months

Pregnant women

Prisoners

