Because the trial data are hierarchical in nature (repeated measures of the same patient nested within participating surgeons/sites), we will use hierarchical generalized linear latent and mixed models (GLLAMM) to analyze the trial data. The model will consider information at the patient and surgeon levels. The basic unit of analysis is at the patient level. Patients nested within the surgeon/site will be considered exchangeable, and sites/surgeons are considered independent from each other. To account for potential imbalance in site/surgeon and patient characteristics, we will adjust for surgeon/site and patient factors in the regression models. Candidate patient level covariates include joint pain severity, pre-decision physical function level, and comorbid conditions, such as diabetes, renal disease, pulmonary disease, depression, obesity, or congestive health failure. Candidate surgeon variables for adjustment include annual surgical volume, procedure type, or geographic region of US. We will follow the parsimonious principle to derive the final models for evaluating intervention effects. First, we will use GLLAMM models to analyze the association of each plausible patient-and site/surgeon-level factor with the outcomes (quality of decision, change in pain severity, function). Those statistically significant variables ($p < 0.10$) will be included in a subsequent analysis using multivariable models to identify a parsimonious set of independent patient-and site/surgeon-level covariates. Model development will be guided by clinicians and patient advisors to assure that clinically important variables are included. To identify independent site/surgeon-level variables, we will include each of the significant variables separately while forcing the patient-level covariates into the models. The significance of each site/surgeon-level variable will be determined using (partial) likelihood ratio tests. We will identify a subset of site/surgeon indicators that contribute to outcomes ($p < 0.10$), independent of individual-level factors. Furthermore, this subset of significant indicators

INVESTIGATOR STUDY PLAN

12.14.2021

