will be entered into the same model in order to assess their contributions to the outcome under analysis, after adjusting for each other, as well as the patient-level covariates. Model assumptions will be carefully examined. In these model-building processes, effect modifications will be examined by including interaction terms between relevant covariates, and to ensure the heterogeneity of the intervention effects among patient subgroups are adequately considered. The analyses will be conducted with all patients; and then for TKR and THR patients separately. While the primary goal is to understand patient-level covariates with outcomes, it is critical to assess surgeon/site factors that may influence outcome for all, or sub-groups of patients. For example, obese, diabetic patients with cardiac disease may have more positive decision quality and pain relief with a more experienced high-volume surgeon.

Aim 2: To assess the effect of OA Careplan on (a) decision quality and (b) pre-to- post decision pain relief and functional gain, we will do the following. We expect 20 surgeons and 2000 patients will receive the OA Careplan intervention, and another 20 surgeons and 2000 patients will receive usual care. The analyses will be conducted with all patients; and then for TKR and THR patients separately. First, we will tabulate the decision quality and care outcomes by arm and for select patient subgroups (e.g., sex, age, race/ethnicity). Second, we will use GLLAMM to estimate adjusted Careplan intervention effects by including in the models a Careplan indicator (Careplan intervention=1 vs. usual care=0) and a set of site/surgeon and patient variables for adjustment. A statistically significant coefficient of the Careplan indicator signals possible intervention effect. In this analysis, interaction terms between the Careplan indicator and surgeon or patient factors will be examined, statistically significant interaction terms may suggest the existence of heterogeneity in intervention effects. If present, intervention effects will be analyzed and presented by subgroups.

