Aim 3: To evaluate the effect of the OA Careplan+Support (Coaching) on (a) decision quality and (b) pre-to-post decision pain relief and functional gain, we will do the following. The 20 surgeons (and their patients) who received usual care in Aim 2 will receive the OA Careplan intervention (n=2,000) in Aim 3. The 20 surgeons who received the OA Careplan in Aim 2 will now receive the OA Careplan+Support (n=2,000 new patients) in Aim 3. Additional surgeons will be recruited and randomized to the 2 arms. First, we will compare patient characteristics between users and non-users of the SUPPORT. We will then identify patient as well as site/surgeon determinants of the use of the SUPPORT using multi-level logistic regression models, and estimate individual patient's probability (propensity) for any use of SUPPORT strategies. Because use of the SUPPORT is not randomized, we will use inverse propensity weighting approach to estimate the effects of the SUPPORT on outcomes (decision quality, pain, function).

We will begin with descriptive analysis, and estimation of crude OA Careplan+Support intervention effects, overall and by select patient subgroups. We will further use GLLAMM to estimate covariate---adjusted intervention effects, overall and by patient

INVESTIGATOR STUDY PLAN

12.14.2021

subgroup, and adjust for propensity scores, plausible surgeon and patient factors. Statistically significant differences between the two arms indicate possible incremental SUPPORT intervention effect beyond the OA Careplan alone. We will conduct pre-post comparisons of the outcomes (decision quality, pain relief) for patients of the 20 surgeons who were in the OA Careplan intervention arm in Aim 2 and are now in the OA Careplan+Support arm.

Statistically significant pre-post changes in outcomes support possible incremental effects of the SUPPORT intervention. We will derive a usage score of the SUPPORT system (e.g., frequency and duration of use) as an indicator of “dosage” of use and use it to estimate a possible “dose-response” relationship between level of use and patient outcomes in the GLLAMM. We will also identify relevant patient-and site/surgeon predictors of any and higher levels of usage.

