Second, we will use GLLAMM to analyze the differences in joint pain and function at 6 and 12 months after the care decision between OA Careplan and comparison arms. We will pool data from both arms in the two phases. We will include an indicator variable to represent intervention status (usual care, OA Careplan, or OA Careplan+Support). We will assess whether 6 and 12 month pain differ between intervention arms. Next, we will repeat this process for the patients with meaningful (>17 point) change in HOOS/KOOS pain score. We expect pain relief will be significantly improved in the OA Careplan arm, with greater improvement to occur in the OA Careplan+Support, compared to the usual care group. Finally, we will formally test the mediation effects of Careplan and Careplan+Support on pain relief and functions at 6 and 12 months, using the two level structural equation models with mediation effects by Krull and MacKinnon (2001) and Preacher, Zyphur and Zhang (2010).

Only those listed in our IRB application will have access to identified data.

At this time, there is no plan to destroy the Patient Reported Outcome (PROs) data because of the value to this data regarding national norms for PROs for patients electing to have surgery and those electing non-surgical management of OA.

PHI including individual contact information for follow-up date collection will be destroyed after all surveys have been completed by individual patients 3 years after the completion of the study.

Published data derived from this study will consist of statistical analyses collapsed (averaged) across participants. Under no circumstances will data from individual participants be identifiable in reports or published manuscripts.

INVESTIGATOR STUDY PLAN

12.14.2021

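### The pooled Aim 2 and Aim 3 model has no phase term, so most of any shift between phases is credited to each intervention step; the pre-post comparison has no concurrent control

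*Combined protocol and SAP*

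**What the plan says.** All of this is in section 13 (Data Analysis and Management) unless noted.

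- **Allocation in Aim 3.** Surgeons who gave usual care in Aim 2 move to the Careplan. For the others, "The 20 surgeons who received the OA Careplan in Aim 2 will now receive the OA Careplan+Support". Additional surgeons are randomized to the two Aim 3 arms.
- **Pooled model.** "We will pool data from both arms in the two phases. We will include an indicator variable to represent intervention status", with three levels: usual care, Careplan and Careplan+Support.
- **Covariates.** Patient candidates are pain severity, function and comorbid conditions. On the surgeon side, "Candidate surgeon variables for adjustment include annual surgical volume, procedure type, or geographic region of US". Candidates are screened at p<0.10, and "We will follow the parsimonious principle to derive the final models for evaluating intervention effects". Phase, aim and calendar time are not listed.
- **Pre-post comparison.** The 20 surgeons moving from Careplan to Careplan+Support are compared before and after, with no comparison group. The stated reading is: "Statistically significant pre-post changes in outcomes support possible incremental effects of the SUPPORT intervention".
- **Concurrent contrasts.** Each aim also has its own between-arm comparison. For Aim 2, "A statistically significant coefficient of the Careplan indicator signals possible intervention effect". For Aim 3, "Statistically significant differences between the two arms indicate possible incremental SUPPORT intervention effect beyond the OA Careplan alone".
- **What changes between phases.** Section 9 gives about 1.5 years of recruitment for each aim. Section 6 widens Aim 3 eligibility ("Aim 3 modification: We proposed to PCORI (and they agreed) that we expand beyond" patients new to the practice) to existing patients attending for a new evaluation.

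**The concern.** Intervention level rises with phase by design. A model that contains intervention status and no phase term has to explain a change in outcomes between phases through the intervention coefficients. If outcomes drift upward, the expected ordering (usual care, then Careplan, then Careplan+Support) can appear when neither intervention works. If they drift downward, real effects can be hidden.

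The pre-post comparison is more exposed still, because all of any shift goes to Support. No group can serve as its control: the other 20 surgeons change intervention at the same time.

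A shift is plausible, but its size is not documented. The one change clearly tied to Aim 3 is the wider eligibility. COVID-19 measures were to start around September 2020 (section 8), but no date is given for the switch from Aim 2 to Aim 3, so COVID-19 as a between-phase change is an inference. Dropping Spanish speakers is negligible, at under 1% of eligible patients (section 6).

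**Working it through.** **Inputs from the documents.** ICC 0.02; 5% significance level; SD 20.8 for knee pain and 20.9 for hip pain; planned difference 3.3 points (all section 13). 3000 patients per aim (section 4). 20 surgeons per sequence (section 13).

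**Assumptions.** 40 carried-over surgeons, so m = 3000/40 = 75 patients per surgeon per phase. Two-sided test, no dropout, no true effects. Phase shift s of 0.02, 0.05 or 0.10 SD.

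**1. The plan's own figure.** With 100 patients per surgeon, the design effect is 1 + 99×0.02 = 2.98 and the effective n is 2000/2.98 = 671 per arm. The SE is 20.8×√(2/671) = 1.135 points. Power at 3.3 points is 82.8% (knee), or 82.4% with SD 20.9 (hip). The stated 80% or more is reproduced.

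**2. Share of a phase shift credited to each step.** Let A1 and A2 be the mean outcomes of the usual care→Careplan surgeons in phases 1 and 2, and B1 and B2 those of the Careplan→Support surgeons.

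- The variance of one surgeon-phase mean is v = 0.02 + 0.98/75 = 0.03307.
- The correlation of a surgeon's two phase means is L = c×0.02/v, where c is the correlation of surgeon effects between phases. At c = 1, L = 0.605.
- Without a phase term, the model assumes that A2 and B1 (both Careplan) have the same expectation. Generalized least squares then gives Careplan vs usual care = (B1 − A1) + [(1+L)/2]×(A2 − B1).
- Under a pure phase shift, B1 − A1 has expectation 0 and A2 − B1 has expectation s. The step is therefore biased by s(1+L)/2. By symmetry the same holds for Support vs Careplan, and Support vs usual care is biased by s(1+L).

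**3. Standard errors (SD units, c = 1).**

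| Contrast | No phase term | With phase term |
|---|---|---|
| Adjacent step | √{(v/20)[2 − (1+L)²/2]} = 0.034 | √(2v/20) = 0.058 |
| Support vs usual care | √{(v/20)×2(1 − L²)} = 0.046 | √{4v(1+L)/20} = 0.103 |

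**4. Results with no phase term and no true effect.**

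| c | Share per step | Support vs usual care | Adjacent step significant, s = 0.05 | s = 0.10 |
|---|---|---|---|---|
| 1 | 0.80 | 1.60 | 22% | 65% |
| 0.8 | 0.74 | 1.48 | 16% | 49% |
| 0.5 | 0.65 | 1.30 | 12% | 32% |

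At s = 0.02 and c = 1 the rate is about 7%. In knee pain points, the bias per step is 0.80×0.05×20.8 = 0.8 or 0.80×0.10×20.8 = 1.7, a quarter to a half of the planned 3.3.

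A REML simulation with estimated variances (600 runs per setting) at s = 0.10 gave 58%, 48% and 35% for c = 1, 0.8 and 0.5. With a phase term it gave 4–7% throughout.

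**5. Surgeon numbers.** The documents give different Aim 3 totals. With 30 carried-over and 8 new surgeons the shares are 0.82 (Careplan vs usual care) and 0.74 (Support vs Careplan). With 40 carried-over and 14 new they are 0.82 and 0.72.

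**6. Pre-post comparison.** The bias is the whole of s. The SE is √{[2×0.98/75 + 2×0.02×(1 − c)]/20} = 0.036, 0.041 and 0.048 for c = 1, 0.8 and 0.5. Rejection is 28%, 23% and 18% at s = 0.05, and 79%, 68% and 55% at s = 0.10.

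**7. With a phase term.** The adjacent estimates become B1 − A1 and B2 − A2, and the bias is zero.

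**The case against.** **The main questions already have phase-free tests.** Sections 4 and 10 ask two pairwise questions, and section 13 plans a concurrent contrast for each. No trend test or three-way endpoint is specified. This stands and limits the severity. But pain and function are primary outcomes in section 10, and the pooled model is the only analysis that sets all three conditions side by side. A biased result there could contradict the within-aim results or be quoted over them.

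**Surgeons may be re-randomized for Aim 3.** Section 4 speaks of randomizing 36–40 surgeons for Aim 3, whereas section 13 moves each surgeon up one step. With 40 surgeons re-randomized and m = 75, the share falls to 0.62 per step (0.57 at c = 0.5). Rejection at c = 1 falls to 13% and 37% for shifts of 0.05 and 0.10 SD. The problem is smaller but remains.

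**The share depends on the ICC and cluster size.** At ICC 0.01 it is 0.72. With about half the patients per surgeon, as in separate knee and hip analyses, it is also 0.72. As the ICC approaches 0 it approaches one half. This is correct; at the plan's ICC, every layout tried gives more than half.

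**Covariates may help.** Adjustment for baseline pain, function and comorbidity could absorb part of a case-mix shift; this was not modelled. It does not deal with secular change. The lists are worded as candidates, so a phase term is not forbidden, but neither is it guaranteed.

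**The fix adds little information.** This is true in the 40-surgeon layout: the adjacent contrasts then equal the within-aim ones. The extra precision of the pooled model came from assuming that there is no phase effect.

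**Conclusion.** The concern holds and should be fixed. As written, the pooled model credits 0.80 of any phase shift to each step and 1.60 to Support versus usual care. The per-step share is 0.65–0.74 if surgeon effects correlate 0.5–0.8 between phases, and 0.57–0.62 if surgeons are re-randomized. The pre-post comparison credits all of the shift to Support. These shares rest on the plan's ICC of 0.02 and about 75 patients per surgeon per phase; they do not depend on the size of the shift. The false-positive rates do depend on it, and the shifts of 0.02–0.10 SD are assumptions. The concurrent comparisons within Aim 2 and within Aim 3 are not biased by phase.

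**What to change.** In section 13:

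1. Force a phase (Aim 2 vs Aim 3) or calendar-time fixed effect into the pooled GLLAMM, exempt from the p<0.10 screening and the parsimony rule. It is estimable because Careplan occurs in both phases, provided that surgeon effects are random. In the 40-surgeon layout, fixed surgeon effects together with a phase term would not identify the steps.
2. Add a surgeon-by-phase random effect, and new-versus-existing-patient status where it is recorded.
3. Label the pre-post comparison descriptive and delete the sentence that reads its significance as support for a Support effect.
4. Base the Support conclusion on the concurrent Aim 3 between-arm contrast.

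Do not replace the pre-post comparison with a difference-in-differences against the other 20 surgeons. They move from usual care to Careplan, so the result would be the Support increment minus the Careplan effect, which is zero if both steps help equally.

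**Cost.** SAP wording and two or three model terms. The only data needed are enrolment date, phase and visit type. Adjacent standard errors rise from 0.034 to 0.058 SD, the single-phase value; the 80%-power detectable difference is 2.8×0.0575×20.8 = 3.35 points, close to the planned 3.3. Support versus usual care rises from 0.046 to 0.103 SD, with a detectable difference of 2.8×0.103 = 0.29 SD, about 6 points. The plan should state that this last contrast is imprecise.

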12. DATA AND SPECIMEN BANKING*

No specimens will be banked for future use. See #13, Data Management, for data retention and access.

13. Data Analysis and Management*

Responsibility for 6 month and 12 month outcome data collection was transferred from UMMS to Northwestern during 2021. At the completion of study enrollment (on or about March 1, 2022), the UMMS data enrollment and collection services will be completed. At that date, the UMMS data center will have already, or will then, transfer all enrollment, patient-reported, and study data to Northwestern for the analytic team to manage and analyze. The UMMS data center will confirm that they expunged all ASK study data from the web-based data capture systems (DatStat, RedCap) and UMMS data storage files within UMMS.

Aim 1

We will transcribe recorded interviews and code using content analysis techniques to identify themes. We expect to achieve data saturation at or before completing 30 interviews with patients and 30 with caregivers.

AIM 2 and 3. Sample size and effect size estimates:

The trial is designed with $\geq 80\%$ statistical power at 5% significance level to detect intervention effects that are meaningful to both patients and surgeons, and health systems. In total, 40 (Aim 2) or 54 (Aim 3) surgeons will be randomized equally to treatment and control arms with an average of 100 patients/surgeon. Based on data from FORCE-TJR, the intraclass correlation within surgeon is approximately 0.02. Using two independent group t-tests adjusting for within surgeon clustering, the trial can detect an intervention effect of (a) improved decision quality of >0.16 SD ; (b) improved quality of OA care defined in two ways: 6 month post-decision pain relief (KOOS/HOOS) of ≥ 3.3 points for TKR patients (34.1 vs. 37.4; SD=20.8) and ≥ 3.3 for THR patients (45.7 vs. 49.0; SD=20.9) or greater proportion of patients with meaningful pain relief (17 points in HOOS/KOOS pain score) of $\geq 6.1\%$ more TKR patients (77.9% vs. 84.0%) and $\geq 4.2\%$ more THR patients (90% vs. 94.2%).

Aims 2 and 3: Overview of analytic approach. We hypothesize (Aim 2) that patient/clinician use of the OA Careplan will improve decision quality as well as

INVESTIGATOR STUDY PLAN

12.14.2021

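### The pooled two-phase model and the pre-post comparison have no stated surgeon-by-phase error term; under the plan's patient-and-surgeon structure their within-surgeon standard errors are too small unless surgeon effects are identical in both phases

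*Combined protocol and SAP*

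**What the plan says.** Everything relevant is in section 13 (Data Analysis and Management).

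- **Structure for both aims (overview of analytic approach).** Repeated measures sit within patients, and patients within surgeons or sites. The text states "The model will consider information at the patient and surgeon levels" and "Patients nested within the surgeon/site will be considered exchangeable, and sites/surgeons are considered independent from each other".
- **Aim 3 design.** The 20 usual-care surgeons of Aim 2 move to the Careplan, and the 20 Careplan surgeons move to Careplan+Support, all with new patients. Further surgeons are added.
- **Pre-post comparison.** "We will conduct pre-post comparisons of the outcomes (decision quality, pain relief) for patients of the 20 surgeons" refers to those who move from Careplan to Careplan+Support. No model or error structure is named. A significant change is to be read as supporting a possible incremental effect of Support.
- **Pooled model.** "We will pool data from both arms in the two phases". The model is a GLLAMM whose indicator has three categories: usual care, Careplan, Careplan+Support.
- **Sample size.** One ICC is given ("the intraclass correlation within surgeon is approximately 0.02"), and it is used for a parallel, single-phase comparison ("Using two independent group t-tests adjusting for within surgeon clustering").

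The plan names no phase or calendar term, surgeon-by-phase effect, between-phase correlation or cluster-robust variance. The nearest safeguard is a general sentence that model assumptions will be examined.

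**The concern.** Intervention status is constant within each surgeon-phase cell, and the carried-over surgeons change condition only by changing phase. Any shift in a surgeon's own results between phases therefore lands directly on the within-surgeon contrast. Such shifts average out over about 20 surgeons. A model with one effect per surgeon treats them as patient noise that averages out over all the patients. The standard error of the contrast is then understated. This is a variance problem, separate from any shift in the overall mean between phases.

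Surgeon-specific shifts are plausible on the plan's own account. Each phase takes about 1.5 years to recruit (section 9). Aim 3 widens eligibility beyond patients new to the practice and drops non-English speakers (section 6). Section 8 describes a case-finding route used only at Northwestern and retraining when office staff are away. These changes need not affect every office equally.

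At stake are two analyses that bear on the incremental value of Support. The pooled one uses pain and function, which section 10 lists among the primary outcome measures.

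**Working it through.** **Inputs.** ICC 0.02; 20 surgeons per Aim 2 arm; 100 patients per surgeon (section 13), or 3000/40 = 75 under the revised numbers in section 4. The correlation *r* of a surgeon's effect across phases is not given, so I assume a range of 1.0 to 0.5. Outcomes are in SD units, and type I error is 2Φ(−1.96/ratio), where ratio = true SE / model SE.

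**1. The plan's own figure.** Design effect 1 + 99 × 0.02 = 2.98, so effective n per arm is 2000/2.98 = 671. For 3.3 points with SD 20.8, power is 0.808 (t, 38 df) or 0.828 (normal), which agrees with the stated 80% or more. It concerns one phase only and does not depend on *r*.

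**2. Pre-post, 75 per phase.** Variance of the mean within-surgeon difference over 20 surgeons:
- surgeon-only model: w = 2(0.98)/(20 × 75) = 0.001307, SE 0.0361;
- true: w′ = w + 2(0.02)(1 − r)/20 = 0.001307 + 0.002(1 − r).

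At r = 0.9, w′ = 0.001507, SE = 0.0388, ratio = 1.07 and type I error = 6.8%.

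**3. Pooled model as written (no phase term), 40 surgeons, 75 per phase.** Call the two adjacent steps δ1 and δ2. The within-surgeon differences estimate each step with variance w. The difference between the two groups' surgeon means, doubled, estimates δ1 + δ2 with model variance B = 8(0.02 + 0.98/150)/20 = 0.010613. The model puts weight k = 2w/(2w + B) = 0.1976 on that second source.
- Model variance of one step: [2wB/(2w + B) + 2w]/4 = (0.002097 + 0.002613)/4 = 0.001178, SE 0.0343.
- True variance: [(1 − k)²·2w′ + k²B′ + 2w′]/4, with B′ = 8[0.02(1 + r)/2 + 0.98/150]/20.

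At r = 0.8, w′ = 0.001707 and B′ = 0.009813. The true variance is (0.002581 + 0.003413)/4 = 0.001499, SE 0.0387, ratio 1.13, type I error 8.2%.

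| r (assumed) | Pre-post SE | Pre-post ratio | Pre-post type I | Pooled ratio | Pooled type I |
|---|---|---|---|---|---|
| 1.0 | 0.0361 | 1.00 | 5.0% | 1.00 | 5.0% |
| 0.95 | 0.0375 | 1.04 | 5.9% | 1.03 | 5.8% |
| 0.9 | 0.0388 | 1.07 | 6.8% | 1.07 | 6.6% |
| 0.8 | 0.0413 | 1.14 | 8.6% | 1.13 | 8.2% |
| 0.5 | 0.0480 | 1.33 | 14.0% | 1.30 | 13.1% |

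With 100 per phase, at r = 0.9, 0.8 and 0.5, pre-post gives about 7.4%, 9.9% and 16.8%, and pooled gives 7.2%, 9.4% and 15.7%.

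**4. Smaller ICC.** If covariate adjustment lowered the ICC to 0.01 (an assumption), step 2 at 75 per phase gives 5.9%, 6.8% and 9.5% at r = 0.9, 0.8 and 0.5.

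**5. Adding only a phase fixed effect to the pooled model.** With 40 surgeons there are then four group-by-phase means and four parameters, so each step is estimated by the arm difference within one phase. At 100 per phase, type I error falls to 5.4%, 5.8% and 7.4% at r = 0.9, 0.8 and 0.5. With seven new surgeons per arm (54 in all) it is at most 8.2%. The true SE at 75 per phase becomes √[2(0.02 + 0.98/75)/20] = 0.0575.

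**The case against.** The strongest reply is that this reads silence as specification. The plan never lists its random terms. A surgeon-level random coefficient for phase would also count as information at the surgeon level, and the exchangeability sentence covers the aims in general. The pre-post comparison has no model at all; analysed as paired surgeon-level differences it would have no such error. This stands, and it is why the point is conditional. It does not dispose of the point, because the only structure the plan describes lacks the term and nothing commits the analyst to add it.

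It is also fair that the size rests on a correlation the documents do not give, that there is no error at 1.0, that it is small near 1.0, and that adjusted or joint-specific analyses could show less. The range in the working reflects this.

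Three stronger readings are tempting and not supported:

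- **That the trial's main comparisons are anti-conservative.** They are not affected: the arm contrasts within Aim 2 and within Aim 3 compare different surgeons in one phase.
- **That the plan sets a significance rule for the pooled indicator.** It says only that differences will be assessed and states an expected direction. The significance wording belongs to the pre-post comparison and the Aim 3 arm comparison, and it is hedged.
- **That a surgeon-by-phase term alone cures these analyses.** It corrects precision. Without a phase term the pooled contrasts stay confounded with calendar time, and the pre-post contrast stays so in any case.

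**Conclusion.** The concern holds in conditional form. If the described patient-and-surgeon structure is carried into these two analyses, within-surgeon contrasts have understated standard errors whenever a surgeon's effect is less than perfectly correlated across phases. The direction is certain; the size is not. At ICC 0.02 and 75 patients per surgeon per phase, nominal 5% tests run at roughly 6% to 9% for correlations of 0.95 to 0.8, and at 13% to 14% for 0.5. They run higher with 100 patients and lower with a smaller ICC. These figures assume equal cluster sizes, a normal reference distribution, and 20 surgeons carried over in each group. The omission merits correction before analysis, but it does not threaten the randomised single-phase results or the stated power.

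**What to change.** - **Pooled GLLAMM:** add a phase fixed effect and a surgeon-by-phase random intercept, and take degrees of freedom for the intervention contrasts at surgeon level. The phase term removes most of the inflation (leaving about 5% to 8%) and the confounding with an overall time shift; the random term deals with the rest.
- **Pre-post comparison:** name the model. Use the same surgeon-by-phase structure, or paired surgeon-level differences over the 20 surgeons (20 − 1 = 19 df). Report it as supportive only, because phase and intervention coincide for these surgeons.

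No new data are needed. The cost is wider intervals. At 75 per phase the pre-post SE rises from 0.036 to between 0.039 and 0.048 SD for correlations of 0.9 to 0.5. The pooled step SE rises from the 0.034 the model would report to about 0.058 SD with 40 surgeons, so the pooled model then says little more about each step than the single-phase comparisons already do.
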